4 OBJECTIVES

4.1 Context for MAL-095 Objectives Relative to MAL-094 Parent Protocol Objectives

The primary efficacy objective of MAL-094 assesses relative vaccine efficacy against clinical malaria over one year post Dose 3 of the Group 4 fractional dosing regimen versus the standard RTS,S/AS01E regimen. Note that the latter standard regimen consists of pooling participants in Groups 2 and 3, as these groups have the same vaccination schedule through the Month 14 visit, and the randomization principle holds. The MAL-094 study additionally includes secondary objectives to study vaccine efficacy and relative vaccine efficacy against clinical malaria and infection for all of the study arms.

A central contribution of MAL-095 is to provide more robust and extensive assessment of vaccine efficacy and relative vaccine efficacy against molecularly confirmed malaria infection. The MAL-095 study is the first trial to rigorously study vaccine efficacy and relative vaccine efficacy against malaria infection using molecular techniques. MAL-095 uses an analysis structure that gives special attention to the comparison of novel RTS,S/AS01E vaccine regimens to the standard RTS,S/AS01E regimen, as noted below.

4.2 Primary Objective

The primary objective of MAL-095 is to estimate and compare vaccine efficacy (VE) against new molecularly confirmed malaria infection(s) across parasite genotypes among the vaccine arms of the trial, using amplicon sequencing and genotyping to detect new infections (see Section 5.1.3 for the definition of a new infection). Infections will be detected by molecular methods from monthly samples or samples collected at unscheduled visits for clinical assessment.

Throughout, vaccine efficacy refers to a comparison of a study endpoint between an active RTS,S vaccine regimen (one of Groups 2 through 5) vs. the rabies control arm, and relative vaccine efficacy refers to a comparison of a study endpoint between two active RTS,S vaccine regimens (among Groups 2 through 5). Vaccine efficacy and relative vaccine efficacy are assessed based on two types of outcomes:

(Primary endpoint 1) first new molecularly confirmed *P. falciparum* infection detection over a specified follow-up period;

(Primary endpoint 2) all new molecularly confirmed *P. falciparum* infection detections accumulated over a specified follow-up period.

As stated in the MAL-095 protocol, vaccine efficacy and relative vaccine efficacy against each primary outcome type will be assessed in analyses of both the ATP and TVC cohorts, as co-primary objectives.

The follow-up periods for assessing the two outcome types in the primary and exploratory analyses, for each of the ATP and TVC cohort analyses, are specified in Section 5.

4.3 Exploratory Objectives

The following exploratory objectives will be addressed for both outcome types:

1. Exploratory objective 1: To assess whether and how VE against new malaria infection based on molecular detection (active case detection) depends on genotypic characteristics of the exposing malaria parasites.
2. Exploratory objective 2: To study whether and how prior infection and/or vaccination has a relationship to subsequent infection by measuring the molecular Force of Infection (mol[FOI]) and assessing the relationship between mol[FOI] and subsequent malaria infection risk. The variable mol[FOI] is defined in Section 6.
3. Exploratory objective 3: To assess whether and how prior infection by a particular parasite genotype, not necessarily a 3D7 vaccine genotype, reduces the likelihood of re-infection by a parasite with the same genotype.

5 STUDY ENDPOINTS

5.1 Primary Endpoints

5.1.1 Definition of New Malaria Infection

Following vaccination, the study will distinguish new from existing infections using an amplicon sequencing-based strategy that involves deep sequencing of small, highly variable regions of the parasite genome. This sequencing allows both:

1. highly sensitive detection of parasitemia (analogous to conventional PCR-based detection), and
2. identification of genetically distinct parasite populations within and between affected individuals.

A new molecularly confirmed malaria infection endpoint is defined by a detected new infection from genomic analysis of dried blood spot samples originating either from active monthly screening for infection or from unscheduled visits intended for the assessment of clinical malaria; thus, molecular detection of a new malaria infection measures either an asymptomatic/subclinical or clinical malaria infection. Later in this section the definition of “new malaria infection” is provided.

Genotype data for the *P. falciparum* circumsporozoite (CS) C-terminus and SERA2 loci are measured from each dried blood spot sample, from which the observed haplotype(s) at each amplicon following filtration of PCR and sequencing errors are defined. However, data from certain samples at certain study visits may be missing or excluded from the final data analysis, for reasons including the sample: is not collected; is not collected with full or clear identification; does not yield any parasite genetic material upon process; or does not yield a clear and unambiguous genotyping result for any reason. In other words, for some samples it will not be possible to define the observed haplotype(s) at each amplicon in a sufficiently reliable fashion to use the data for analysis.

Associated with each sample with molecular detection of malaria infection is the complexity of infection (COI), defined as the maximum of (i) the number of unique haplotypes for the CS C-terminus amplicon, and (ii) the number of unique haplotypes for the SERA2 amplicon in the sample. It is expected that the cause of $n = COI > 1$ is multiple distinct malaria infections; thus, COI itself is one estimate of the number of new molecularly confirmed malaria infections that have occurred up to the time of the given sample. However, simultaneous super-infection is possible, and some new malaria infections could be undetected if enough time elapses between infection and sampling, or if antimalarial treatment clears an infection.

The following paragraphs provides more detail on the definition of a new malaria infection.

Malaria infection

A *P. falciparum* infection is defined as amplicon nucleotide sequence-based parasite positive status defined as detection of at least one haplotype supported by at least 50 nucleotide sequence reads and 1% of total reads for at least one of the two amplicons.

New malaria infection

As there is no guarantee of complete clearance of infections, a new infection may originate from a post-enrollment sample that goes from negative to positive, or from a post-enrollment sample that contains a new haplotype that was not previously observed in several previous samples from the same participant. A new infection for the primary objective is defined as at least one of the haplotypes in the post-enrollment sample not being detected in the previous three samples drawn from the same participant regardless of the visit type (scheduled or unscheduled). An exception is made if a haplotype is detected in the first post-enrollment sample not collected on the day of enrollment, in which case it counts as a new infection if the same haplotype was not detected in the single sample from the enrollment visit. Haplotype detection requires observation of at least 50 reads and 1% of total reads supporting the haplotype within a sample. Note that a molecularly confirmed infection in a sample from the enrollment visit does not count as a new infection because the sample was collected prior to administration of the first dose, and therefore the sample should not contribute to measuring the vaccine effect. A molecularly confirmed infection in a sample from an unscheduled visit that occurred on the day of enrollment does not count as a new

infection either because we cannot rule out that it is a persistent infection acquired prior to enrollment.

5.1.1.1 Modified Definition of Molecular Parasite Positivity for Month 32 Analyses

During inspection of sequencing data in support of the M20 interim analysis, a post hoc decision was made to revise the minimum read count for calling a haplotype as present in a sample from 50 to 325 sequencing reads. The 50 read threshold established during formulation of the original SAP v1.0 was chosen to optimize precision and recall using a truth set of sequencing data from mock samples. However, upon analysis of the much larger M20 trial dataset, it was determined that a revised threshold of 325 reads would more effectively reduce signals of false positive haplotype calls due to sporadic transfer of DNA among samples within sequencing batches housed in the same multi-well plate.

5.1.2 Definition of Primary Endpoint 1

We define the time to primary endpoint 1 variable as the number of days from the time origin in each analysis to the visit date associated with the first molecular detection of a new malaria infection, irrespective of

- the number of missed scheduled visits preceding this event,
- whether this event occurred within a certain time interval following the onset of antimalarial treatment, and/or
- an earlier occurrence of secondary-case clinical malaria (with no molecular detection).

For participants with no molecular detection of a new infection at any visit within a considered follow-up period, their time to primary endpoint 1 will be right-censored at the collection date of the last parasite negative sample within the follow-up period in each analysis.

5.1.3 Definition of Primary Endpoint 2

For a participant with no missed scheduled visits and no missed samples from attended visits, we estimate the total number of new molecularly confirmed malaria infections in a given follow-up period as the number of occurrences of molecular detection of a new malaria infection during this period regardless of

- whether any such detection occurred within a certain time interval following the onset of antimalarial treatment, and/or
- any occurrence(s) of secondary-case clinical malaria.

For a participant with missed scheduled visits or missed samples from attended visits, the definition of an observed/known primary endpoint 2 in a given follow-up period accounts for missing sequence data, and the definition is stated in Section 7.6.1.

A descriptive sensitivity analysis will be conducted to compare rates of primary endpoint 1, defined in Section 5.1.2, to those of first new infection by either molecular detection or passive detection of secondary-case clinical malaria per the MAL-094 protocol

definition. The descriptive analysis will include tabulating proportions of molecularly detected new infections that are in samples from visits with confirmed secondary-case clinical malaria, and proportions of negative samples for clinical malaria ascertainment that yielded a positive result by the molecular method of detection. Clinical case detection is not included in the primary endpoint definitions under the premise that each infection requires a molecular presentation. Because an infection that was acquired pre-enrollment may first clinically manifest after enrollment, ignoring clinical cases in primary endpoint 1 precludes from erroneously calling a clinical infection the first new infection. Also, ignoring clinical infection events avoids double-counting of infections in primary endpoint 2.

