3 STUDY COHORTS

Analyses will be conducted in two distinct study cohorts:

(Cohort 1) The According-To-Protocol (ATP) cohort includes all participants who received the first three vaccinations according to the MAL-094 protocol procedures and who are observed to be at risk for a molecularly confirmed malaria infection at 14 days post-Dose 3.

(Cohort 2) The Total Vaccinated Cohort (TVC) is all participants who received at least one dose of a study vaccine.

Primary and exploratory analyses of vaccine efficacy will be conducted both in ATP and TVC cohorts, with participants analyzed according to the as-treated principle (i.e., actually received treatments). The same ATP cohort will be analyzed in vaccine efficacy analyses of both primary study endpoints defined in Sections 5.1.4 and 5.1.5.

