5.1.4 Primary Endpoints Assessed during Primary Follow-up

The two primary endpoints for the ATP cohort analyses are:

1. Time from 14 days post-Dose 3 to molecular detection of the first new malaria infection through to 12 months post-Dose 3
2. Number of new molecularly confirmed malaria infections during the same follow-up period used for ATP primary endpoint 1

The two primary endpoints for the TVC analyses are:

1. Time from first vaccination to molecular detection of the first new malaria infection through to the Month 20 study visit post first vaccination
2. Number of new molecularly confirmed malaria infections during the same follow-up period used for TVC primary endpoint 1

For the measurement of new malaria infection detection endpoints in the ATP cohort, “through to xx months post-Dose 3” (e.g., xx=12 months) means through to the Month yy study visit (e.g., if xx=12, then yy=14 for Groups 1-4 and yy=19 for Group 5). This approach rather than measurement of exactly xx months post-Dose 3 (irrespective of visit date) is used to ensure that follow-up for all study arms only includes time periods before Dose 4, which is administered at the Month 14 study visit for Groups 3 and 4 and at the Month 20 study visit for Groups 2 and 5. If the Month yy visit is missed, the time-to-event is right-censored at the last parasite negative sample collection date prior to the missed Month yy visit.

For analyses of the TVC, for both primary endpoints, new molecularly confirmed malaria infections are counted after the first vaccination through to the Month 20 visit, for all study arms and all comparisons. Infections detected in any sample collected on the day of enrollment (whether from the enrollment visit or an unscheduled visit completed on the day of enrollment) are excluded, i.e., not treated as new infections for either primary endpoint because, in these samples, we cannot rule out a persistent infection acquired prior to enrollment.

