An additional secondary analysis will estimate cumulative distributions of the time to the first molecular detection of a new malaria infection by study group. The cumulative distribution functions will be estimated in two ways: first, by using the Nelson-Aalen estimator for the cumulative hazard function, and second, by adjusting for other baseline participant characteristics via targeted maximum likelihood estimation (TMLE, Moore and van der Laan, 2009). The latter fully covariate-adjusted method is especially relevant for the ATP analysis, as described above. This analysis uses as an intermediate step an estimate of the distribution of the time to the first molecular detection of a new malaria infection conditional on baseline covariates (listed in Section 6.2), which is produced using the Super Learner method (as implemented in R packages *SuperLearner* or *s3*). Given the possibility of our requiring resampling methods (e.g., nonparametric bootstrapping) to obtain inference, we may restrict the Super Learner library of candidate regression methods to those that are computationally stable and run relatively quickly. For example, these candidate regressions will include regressions based on several different generalized linear models that include up to two-way interactions between covariates and treatment.

The estimated cumulative distribution functions of the time to the first molecular detection of a new malaria infection will be plotted with 95% pointwise and simultaneous

confidence intervals, through to the last time point in the specified time period. Similarly, point estimates and 95% confidence intervals will be produced for additive differences and cumulative incidence-based vaccine efficacy or cumulative relative risk contrasts between the two study groups being compared. These analyses will be done for each individual and pair of study groups specified in Table 5, analogously to the analysis of instantaneous kernel-smoothed hazard functions and their contrasts.

7.5.1 Handling of Loss to Follow-up for Primary Endpoint 1

Cox proportional hazards models and nonparametric inference on instantaneous hazard ratios over time

Regarding loss to follow-up, for both TVC and ATP cohort analyses, for each participant included in the analysis, the right-censoring time is defined as the last parasite negative sample collection date recorded during the follow-up period under study. The assumption of random censoring is needed for valid inferences.

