9.4.2 Inferential Analysis of Potential VE Modifiers of Interest

Cox proportional hazards models, adjusted for baseline covariates, will be used for analysis. Assessments of vaccine effects within the baseline positive subgroup and within the baseline negative subgroup in the TVC or ATP cohort are valid based on randomization. If M2-FOI is uncorrelated or negligibly correlated with treatment assignment in the ATP cohort, assessments of vaccine effects separately within categories of M2-FOI = 0 and M2-FOI > 0 in the ATP cohort are approximately valid based on randomization, and there is minimal risk of post-randomization selection bias induced by subsetting on M2-FOI = 0 vs. M2-FOI > 0. Given that few participants with M2-FOI > 1 had first new malaria infection endpoints, statistical inferences studying M2-FOI analyze M2-FOI as a dichotomous variable $I(M2\text{-FOI} > 0)$, interpreted as whether an intercurrent new malaria infection occurred after the first vaccination and by the third vaccination.

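### Endpoint 1 censors event-free children at their last parasite-negative sample, although the event is a new haplotype, so a child carrying only already-seen haplotypes can have no censoring date

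*SAP*

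**What the plan says.** SAP 5.1.2 covers participants with no molecular detection of a new infection in the follow-up period: "their time to primary endpoint 1 will be right-censored at the collection date of the last parasite negative sample within the follow-up period". SAP 7.5.1 repeats this for both cohorts ("the right-censoring time is defined as the last parasite negative sample collection date recorded during the follow-up period under study") and adds: "The assumption of random censoring is needed for valid inferences". SAP 5.1.4 does the same when the final ATP visit is missed: "the time-to-event is right-censored at the last parasite negative sample collection date prior to the missed Month yy visit". The TMLE part of 7.5.1 takes over the same censoring definition.

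SAP 5.1.1 defines the two states differently. A sample is positive if at least one haplotype, new or old, reaches the read threshold. A new infection is "defined as at least one of the haplotypes in the post-enrollment sample not being detected in the previous three samples". The same section accepts that infections may not clear completely and does not count an infection found at enrolment as new.

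On cohort entry, SAP 3 says the TVC "is all participants who received at least one dose of a study vaccine". The ATP cohort takes children who had the first three vaccinations per protocol and "who are observed to be at risk for a molecularly confirmed malaria infection at 14 days post-Dose 3".

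**The concern.** Parasite-negative and free of a new infection are not the same thing under 5.1.1. A sample that shows only haplotypes already seen in the previous three samples is neither an event nor negative. The censoring rule uses only negative samples, so it ignores valid observations that no event has occurred. Two kinds of children are affected:

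- A child with no negative sample in the window has no value for a primary endpoint variable.
- A child with an early negative sample followed by persistent old haplotypes is censored too early.

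The variable feeds the Cox, kernel-smoothed and TMLE analyses. The result therefore depends in part on a programming choice that the SAP does not record. If software drops children with a missing time, a carrier who later shows a new haplotype stays in with an event, while an otherwise similar carrier who never does disappears. Inclusion then depends on the future outcome, which conflicts with the random censoring that 7.5.1 requires.

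**Working it through.** **1. The rules applied to constructed histories.** The plan has no figure of its own to reproduce here. A is one haplotype. Samples are monthly.

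| Window and history | Event in window | Date under the SAP rule | Last sample without a new haplotype |
|---|---|---|---|
| TVC, A at M0 to M20 | none | none | Month 20 |
| TVC, A at M0 to M2, then lost | none | none | Month 2 |
| TVC, A at M0, negative M1, A at M2 to M20 | none | Month 1 | Month 20 |
| ATP 2.5-14, negative M0 and M1, A at M2 to M14 | none | none | Month 14 |
| ATP 2.5-14, negative M0 and M1, A at M2, negative M3, A at M4 to M14 | none | Month 3 | Month 14 |

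The third child loses 20 - 1 = 19 observed event-free months and the fifth loses 14 - 3 = 11. Two checks limit the reach of the gap. A TVC child negative at enrolment and positive at M1 has an event at M1, and A returning after three negative samples is an event. In the TVC, then, the gap mainly concerns children already positive at enrolment. In the ATP cohort it concerns children who carry a haplotype into the window, if they are admitted.

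**2. How often a carrier stays undated.** The documents give no carriage duration, so this is an assumption. Let d be the chance per sample of re-detecting the carried haplotype and v the chance of a new one, independent across k samples. The chance that all k samples fall in the gap is (d(1 - v))^k. The low end uses d = 0.5 and v = 0.10, so d(1 - v) = 0.45. The high end uses d = 0.95 and v = 0.02, so d(1 - v) = 0.931.

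| Samples in window | Low | High |
|---|---|---|
| k = 2 (early loss) | 0.45^2 = 20% | 0.931^2 = 87% |
| k = 7 (ATP M3-9) | 0.4% | 61% |
| k = 12 (ATP M3-14) | 0.01% | 42% |
| k = 20 (TVC M1-20) | about 0% | 24% |

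These are chances for a carrier, not for a child drawn from the whole arm.

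**3. Effect on VE (simulation, all inputs assumed).**
- Control infection rate 0.5, 1, 2, 4 or 6 per year, with one unique haplotype per infection.
- Mean carriage 2, 4 or 8 months; detection 100% or 70% per sample.
- Hazard ratio 0.6 in the window, and 0.6 or 0.8 from Dose 1 to window start.
- 0% or 30% of infections treated and cleared; 10% missed visits; 1.5% loss per month; 110,000 children per arm.

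This gives 5 x 3 x 2 x 2 x 2 = 120 scenarios. Baseline positivity was 8-50% in 84 of them, above 50% in 24, and below 8% in 12, where every shift was under 0.1 point. Shifts are in VE points against censoring at the last valid sample, with undated children dropped:

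| Analysis | 8-50% baseline positivity | Above 50%: largest fall |
|---|---|---|
| Groups 2-4 ATP, 12 months | -1.1 to +0.1 | 3.3 (any ATP group) |
| Group 5 ATP, 12 months | -0.9 to +0.7 | as above |
| Groups 2-4 ATP, 7 months | -1.5 to +0.2 | 8.2 (any ATP group) |
| Group 5 ATP, 7 months | -1.0 to +1.8 | as above |
| TVC M0-20 | -0.6 to 0 | 1.2 |
| TVC M0-14 | -1.1 to 0 | 2.6 |

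If undated children are instead censored at their last sample, the shift is 0.0 at full detection and within 0.3 at 70% detection. The early-censored children keep their SAP dates in that comparison, so their lost time has a negligible effect on aggregate VE.

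With no vaccine effect, equal carriage and 8-50% baseline positivity, the shift stays within about 0.35.

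Also at 8-50%, dropping raises control cumulative incidence by up to 3.4 points (ATP 12 months), 6.1 (ATP 7 months) and 0.9 (M0-20). Controls with no negative sample reach at most 6.9%, 13.7% and 3.1%, about 21, 41 and 9 of 300.

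**Example** (1 infection per year, 8 months' carriage, full detection, no treatment, early hazard ratio 0.6). VE under last valid sample / dropped / last sample for undated children only: Groups 2-4 ATP 12 months 40.0 / 39.5 / 40.0; TVC M0-20 38.8 / 38.3 / 38.8; Group 5 ATP 7 months 39.4 / 41.3 / 39.4 (the top of that row's range, within rounding). Control cumulative incidence, Groups 2-4 7-month window: 41.0% / 46.1% / 41.0%.

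**The case against.** **The SAP never says to drop these children.** That is correct. The text leaves the date undefined, and every sizeable shift above assumes that software removes the record. A sensible programmer may already have used the last sample, which does practically no harm. What stands is that neither choice is documented. The only rule that would supply a date is in 8.5.1 (last observed visit before three consecutive missed visits). It is introduced there as a modification for exploratory objectives 2 and 3, so it cannot be read back into endpoint 1.

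**ATP entry may already remove carriers.** It may. A child carrying one haplotype is still at risk of another, so the phrase in SAP 3 does not clearly exclude carriers, but it could be meant to. A reader might infer from 9.4.2 ("Assessments of vaccine effects within the baseline positive subgroup and within the baseline negative subgroup in the TVC or ATP cohort") that carriers are shown to be in the ATP analysis. The documents do not support that. Section 9.4 describes positivity on the day of first vaccination, using a different definition (at least 325 reads, or microscopy). Such children may have cleared by Month 2.5 or 7.5. Its M2-FOI analyses show that an earlier infection does not by itself bar a child from the ATP cohort, but they too are silent on carriage at the time origin. If at risk excludes children positive at the last sample before the window, the ATP shifts fall to within about 0.2 points and the issue lies mainly in the TVC.

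**The affected group may be very small.** A child must never test negative and never show a new haplotype. Protocol 2.4.5 notes that parasites are not continuously present in peripheral blood, and SAP 7.7.1 expects most children to be infected by Month 20. The simulation also leaves out missing single-amplicon data (expected in 20% or more of endpoint 1 cases, SAP 8.2) and false-positive haplotypes, both of which can turn a carrier into an event. Shared common haplotypes push the other way. The counts per 300 are therefore maxima over assumptions, not estimates.

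**Conclusion.** The mismatch between event and censoring rule is real, and it leaves a primary endpoint variable undefined for an identifiable kind of child. It is clear in the TVC, which has no infection-status condition, and conditional in the ATP cohort. Severity is minor.

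If undated children are dropped, cumulative incidence is overstated in each arm. VE moves by about 0 to 2 points, in either direction, under the assumed rates and carriage times with baseline positivity up to 50%. Larger shifts appear only above that. For scale, with 300 per arm the 95% confidence interval around a VE of 40% is roughly 12 to 20 points either side at 12 months. If undated children are censored at their last sample, VE is practically unchanged.

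A reader might go further and conclude that the rule biases VE in the vaccine's favour or could overturn a result. Neither follows. The direction is not fixed: VE tends to fall slightly when carriage is equal between arms, and rises mainly when controls carry clearly more at window start, as in the Group 5 7-month window. The frequency of undated children is not in the documents, and no conclusion is expected to reverse.

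Nor is early censoring of children who have a negative sample always trivial for the child. One constructed history loses 19 months. Only the aggregate effect on VE is negligible.

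**What to change.** In SAP 5.1.2, 5.1.4 and 7.5.1, censor event-free children at the collection date of the last sample in the follow-up period with a valid sequencing result, either parasite-negative or positive only for haplotypes that do not meet the new-infection definition in 5.1.1. A child with no valid in-window sample contributes no at-risk time. Say that a parasite-negative result counts as valid, because 5.1.1 lists samples without parasite genetic material among those that may be missing or excluded.

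Report by arm and window how many event-free children had no negative sample and how they were handled. A sentence in SAP 3 on whether a child still positive at 14 days post-Dose 3 is at risk would settle how far this reaches into the ATP cohort.

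Month 20 results are already known (SAP 9.3 refers to estimated VE). The change should therefore be labelled post hoc and shown beside the rule as now written, as a sensitivity analysis, not in its place. The cost is one derived variable, one table of counts and a small rerun of the endpoint 1 analyses on existing data.
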